7. STUDY PROCEDURE AND ASSESSMENTS

7.1. Study procedures

See table next page

| Visit | S | 1 | 24hrs | 2 | 3 | 4 | 24hrs | 5 | 6 | 7 | 8 | # |
|---|------------------|-----------------------------|---------------------------|----------------------|------|-----------------------------|---------------------------|------|----------------------------|------------------|------------------|-------------------|
| Visit Type | Screening | 1 st Vaccination | Phone Call 1 [†] | FU "Sentinel groups" | FU1 | 2 nd Vaccination | Phone call 2 [†] | FU2 | FU3 End of treatment phase | LTFU1 | LTFU2 EOS | Unscheduled visit |
| Day | -28 to -1 | 0 | 1* | 7±1 | 14±1 | 28±3 | 29* | 42±3 | 56±3 | 91±7 | 210±14 | N/A |
| Signed informed consent | ✓ | | | | | | | | | | | |
| Inclusion/exclusion criteria | ✓ | ✓ | | | | | | | | | | |
| Individual halting rules | | | ✓† | ✓† | ✓ | ✓ | ✓† | ✓ | ✓ | ✓ | | |
| Medical history & vaccination | ✓ | | | | | | | | | | | |
| Prior & Concomitant Medication (including immunization †) | ✓ | ✓ | ✓† | ✓† | ✓ | ✓ | ✓† | ✓ | ✓ | ✓ | ✓ | ✓ |
| Demographic ⁽¹⁾ | ✓ | | | | | ✓ | | | ✓ | | | ✓ |
| Physical examination ⁽²⁾ | ✓ | ✓ | | ✓† | ✓ | ✓ | | | ✓ | | ✓ | ✓ |
| Vital Signs ⁽³⁾ | ✓ | ✓ | | ✓† | ✓ | ✓ | | ✓ | ✓ | ✓ | ✓ | ✓ |
| 12-lead ECG | ✓ | | | | | | | | | | | |
| Randomization / Group allocation | | ✓ | | | | | | | | | | |
| COVID-19 vaccine/ Placebo | | ✓ | | | | ✓ | | | | | | |
| Recording all AEs, AESIs and SAEs | ✓ | ✓ | ✓† | ✓† | ✓ | ✓ | ✓† | ✓ | ✓ | ✓ | ✓ | ✓ |
| Local reaction (Tolerability) | | ✓ | ✓† | ✓† | ✓ | ✓ | ✓† | ✓ | ✓ | | | ✓ |
| Participant diary ⁽⁴⁾ | | ✓ | | ✓† | ✓ | ✓ | | ✓ | | | | |
| Pregnancy test | ✓ ⁽⁵⁾ | ✓ ⁽⁶⁾ | | | | ✓ ⁽⁶⁾ | | | ✓ ⁽⁶⁾ | ✓ ⁽⁶⁾ | ✓ ⁽⁶⁾ | |
| Blood Safety Analysis ⁽⁷⁾ | ✓ | | | ✓† | ✓ | ✓ | | | ✓ | | ✓ | ✓ |
| Breath alcohol and urine drug tests | ✓ | ✓† | | | | ✓ | | | | | | |
| Viral Serology (HBV, HCV, HIV) | ✓ | | | | | | | | | | | |
| SARS-CoV-2 PCR and serology | ✓ | | | | | | | | | | | ✓ ⁽⁸⁾ |
| PBMC collection for immunological assessments ⁽⁹⁾ | | ✓ | | | ✓ | ✓ | | ✓ | ✓ | ✓ | | |
| Serum collection for immunological assessments ⁽⁹⁾ | | ✓ | | | ✓ | ✓ | | ✓ | ✓ | ✓ | | |
| Measles-Ab (ELISA) | | ✓ | | | | ✓ | | | ✓ | | | |
| Measles Shedding ⁽¹⁰⁾ (Blood, urine, saliva, nasal swab) | | ✓† | | ✓† | ✓† | ✓† | | ✓† | | | | |

- (1) **Demographic:** Weight, Height (only at VS), BMI;
 - (2) **Physical examination:** a complete physical examination (including assessment of general appearance, ears / nose / throat; skin; lymph nodes; musculoskeletal/extremities; abdomen; cardiovascular; respiratory; neurological body systems) will be performed at VS, V8. A directed physical examination (i.e. the examination will only be done on one or several body system such as general appearance, ears / nose / throat; skin; lymph nodes; musculoskeletal/extremities; abdomen; cardiovascular; respiratory; neurological body systems in case of symptoms) will be performed at V1, V2 (only for the “Sentinel Groups”), V3, V4, and V6.
 - (3) **Vital Signs:** HR, BP, RR (at rest) and body temperature;
 - (4) **Participant diary:** provided at V1 and V4, filled in up to 14±1 days after each vaccination, retrieved at V3 and V5.
 - (5) **Pregnancy test:** Serum β -human chorionic gonadotropin (β -HCG)
 - (6) **Urine pregnancy spot test**
 - (7) **Safety analysis:** See Appendix 1
 - (8) **In case of presence of COVID-19 symptoms, SARS-CoV-2 PCR should be performed.**
 - (9) **Parameters that will be assessed:** SARS-CoV-2 specific serum antibodies, neutralizing antibodies, staining panel for T cell characterization: (anti-CD3, CD4, CD8, CD45RA, CCR7, INF- γ , TNF- α , IL-5, IL-13, Granzym B).
 - (10) Only the 6 subjects of the “Sentinel Groups” will be part of shedding assessment. Samples (saliva, nasal swab, urine and whole blood) will be collected.
- ⊕ **Including history of measles infection or measles immunization**
- ◆ **Only for “Sentinel Groups”**
- * **A time window of ± 3 hours is allowed**
- ⊕ **only if the screening visit (VS) took place more than 7 days prior to V1**

| Visit | S | 1 | 2 | 3 | 4 | 5 | 6 | 7 | 8 | # |
|---|-------------|-----------------------------|-------------------|-------------|-----------------------------|-------|----------------------------|-------|-------------|-------------------|
| Visit Type | Screening | 1 st Vaccination | FU Sentinel group | FU1 | 2 nd Vaccination | FU2 | FU3 | LTFU1 | LTFU2 EOS | Unscheduled visit |
| Day | -28 to -1 | 0 | 7±1 | 14±1 | 28±3 | 42±3 | 56±3 | 91±7 | 210±14 | N/A |
| Blood Safety Analysis : Hematology | 3 to 4.5 mL | - | 3 to 4.5 mL | 3 to 4.5 mL | 3 to 4.5 mL | - | 3 to 4.5 mL | - | 3 to 4.5 mL | As needed |
| Blood Safety Analysis : biochemistry (*) | 3 to 8 mL | - | 3 to 8 mL | 3 to 8 mL | 3 to 8 mL | - | 3 to 8 mL | - | 3 to 8 mL | As needed |
| Viral Serology (HBV, HCV, HIV) from biochemistry sample | 6 mL | - | - | - | - | - | - | - | - | - |
| Blood Safety Analysis : coagulation | 3 to 3.5 mL | - | 3 to 3.5 mL | 3 to 3.5 mL | 3 to 3.5 mL | - | 3 to 3.5 mL | - | 3 to 3.5 mL | As needed |
| Urine Safety analysis | 5 to 8.5 mL | - | 5 to 8.5 mL | 5 to 8.5 mL | 5 to 8.5 mL | - | 5 to 8.5 mL | - | 5 to 8.5 mL | As needed |
| Blood Pregnancy test | 4.5mL | - | - | - | - | - | - | - | - | - |
| Urine Pregnancy test | - | 1 | - | - | 1 | - | 1 | 1 | 1 | - |
| SARS-CoV 2 PCR | 1 | - | - | - | - | - | - | - | - | As needed |
| SARS-CoV 2 serology | 5 mL | - | - | - | - | - | - | - | - | As needed |
| PBMC collection | - | 100 to 120 mL [†] | - | 50 mL | 100 to 120 mL [†] | 50 mL | 100 to 120 mL [†] | 50 mL | - | - |
| Serum collection for immunological assessments (including Measles-Ab when applicable) | - | 16 mL | - | 16mL | 16 mL | 16 mL | 16mL | 16 mL | - | - |
| Blood Measles virus shedding test | - | 5 mL | 5 mL | 5 mL | 5 mL | 5 mL | - | - | - | - |
| Urine Measles virus shedding test | - | 5 mL | 5 mL | 5 mL | 5 mL | 5 mL | - | - | - | - |
| Saliva Measles virus shedding test | - | 1 | 1 | 1 | 1 | 1 | - | - | - | - |
| Nasal shedding test | - | 2 | 2 | 2 | 2 | 2 | - | - | - | - |
| Max. blood volume drawn "Sentinel Groups" | 31,5 mL | 141 mL | 21mL | 87 mL | 157 mL | 71 mL | 152 mL | 66 mL | 16 mL | As needed |
| Max. blood volume drawn "Main Cohorts" | 31,5 mL | 136mL | - | 82 mL | 152 mL | 66 mL | 152 mL | 66 mL | 16 mL | As needed |
| Max. urine volume collected "Sentinel Groups" | 8.5 mL | 5 mL | 13.5 mL | 13.5 mL | 13.5 mL | 5 mL | 13.5 mL | - | 8.5 mL | As needed |
| Max. urine volume collected "Main Cohorts" | 8.5 mL | - | - | 8.5 mL | 8.5 mL | - | 8.5 mL | - | 8.5 mL | As needed |

*For Belgian site: β-HCG included; 2mL on Na Fluoride for glucose dosage; [†] Blood volume collected will be adjusted to body weight according to 3HREC guideline for maximum paediatric blood volumes for research purpose and will not exceed 120mL.

Table 3: total volume of blood and urine drawn/collected during the study

7.2. Study Visits

7.2.1. Screening visit (VS) (28 to 1 days before randomization)

After providing information on objectives, procedure and potential risk of the study, a sufficient time will be let to healthy volunteers (participant) for questions and answers and reflection as to whether or not he/she wishes to participate. Those willing to participate will be invited to sign an informed consent form and will be assessed for their eligibility to participate in the study. Screening tests will start only after the participant and Investigator have signed the informed consent form (ICF). Screening will take place from 28 days to 1 days prior to injection for the “Sentinel Groups” and to randomization/injection for the “Main Cohorts”.

The following screening assessments will be performed for each participant

- Participant identification
- Record of medical and surgery history (including history of measles infection)
- Record of prior and concomitant therapy (including history of measles immunization)
- Demographics: including Sex; month and year of birth; Height; Weight; BMI (calculated as Kg/m²)
- A complete physical examination
- Vital signs: blood pressure and heart rate (in sitting or supine position*), respiration rate (RR), body temperature,
- 12-lead ECG
- Laboratory safety screens as outlined in Appendix 1 (including blood pregnancy test for female subjects)
- Breath alcohol and urine drug tests (as outlined in Appendix 1)
- HBV; HCV and HIV serology**
- SARS-CoV-2 PCR and serology
- Compliance with inclusion/exclusion criteria

* Vital signs can be measured in sitting or supine position as well as long as within 1 patient the measurements are always done in the same position.

** Results of HBV, HCV and HIV serology will be communicated to participant unless he/she expresses the wish, via the Informed consent form, not to be informed.

At the end of the screening visit, the next visit (Visit 1) will be scheduled and confirmed (once results of laboratory safety test will be available and assess).

During the time window authorized for the screening visit, the Investigator may order a re-test of the following parameters: demographics (Height, weight and BMI), vital signs (HR, RR, BP, body temperature), 12-lead ECG, laboratory safety screen tests, breath alcohol and/or urine drug tests evaluated during the initial screening visit, if they need to evaluate the evolution of that parameter(s) or to confirm the value

observed. Results of this re-test must be available prior to the first administration of the investigational product. The result of the re-test will be considered for subject eligibility.

7.2.2. Visit 1 - Randomization/ first injection (Day 0)

Participant will arrive at the Investigational clinical site of the randomization/vaccination day.

The following assessments will be performed for each participant before first injection for the “Sentinel Groups” and before randomization / first injection for “Main Cohorts”:

- Re-check record of medical and surgery history
- Recording of any changes in the concomitant medications or medical status since screening visit.
- Re-check compliance with inclusion/exclusion criteria
- A directed physical examination
- Vital signs (BP, HR, respiratory rate, and body temperature) measurement in sitting or supine position*
- Urine pregnancy test (for Females)
- Breath alcohol and urine drug tests** (as outlined in Appendix 1)
- Blood sample will be drawn for immunomonitoring analysis
- Collection of saliva, urine, nasal swab and blood for shedding assessment (only for “Sentinel Groups”)

* *Vital signs can be measured in sitting or supine position as well as long as within 1 patient the measurements are always done in the same position.*

** *only if the screening visit (VS) took place more than 7 days prior to V1*

If all criteria are fulfilled, no significant change in the participant’s health, he/she will receive the vaccine for the “Sentinel Groups” or be assigned a study randomization number (see section 4.11) for the “Main Cohorts”. Then, he/she will receive the first intramuscular injection into the deltoid muscle. The time and the arm (left or right) in which the vaccine was injected will be recorded in the participant’s source data and in the eCRF.

After injection, the participants will remain in the Investigational clinical site for medical supervision and monitoring. If they belong to:

- the "Sentinel Groups" for a minimum of 1 hour post-injection.
- the "Main Cohorts" for a minimum of 1 hour post-injection.

The following assessment / activities will be performed after vaccine administration:

For “Sentinel Groups”: at 1 hour (± 15 min) after injection

- Vital signs (BP, HR, respiratory rate, body temperature).
- Assessment of Local reaction of the injection site and general reaction (see Appendix 2) by a study physician, or his/her delegate.

For “Main Cohorts”: at 1 hour (± 15 min) after injection

- Vital signs
- Local reaction of the injection site and general reaction.

During the visit, the Investigator may order one re-test of the following parameters: vital signs (HR, RR, BP, body temperature), urine pregnancy test (for Females), breath alcohol and/or urine drugs test, if they need to evaluate the evolution of that parameter(s) or to confirm the value observed. The reason of this re-test will be documented in the participant’s source data. Results of this re-test must be available prior to the first administration of the investigational product. The results of the re-test will be considered for subject eligibility. The reason and results of this re-test will be documented in the participant’s source data and in the eCRF.

Participant will be provided with a diary, a ruler and a thermometer and they will receive instructions on how to measure temperature and record adverse events during the subsequent 14 ± 1 days after the injection. The diary will be returned on the next visit at investigational clinical site.

Subject will be given an emergency card with a phone number to call in case of questions or upon occurrence of any AE.

At the end of the visit, which lasts approximately 1 hour 30 min in the "Sentinel Groups" and in the "Main Cohorts", once the study physician has determined that he/she is fit to be released, the participant will be discharged from the investigational clinical site. The appointment for the phone call (24 hours ± 3) and for the Visit 2 (day 7 ± 1) for the “Sentinel Groups” and for Visit 3 (Day 14 ± 1) for the “Main Cohorts” will be scheduled and confirmed with the participant.

7.2.3. Phone call 1 - “Sentinel Groups” (Day 1 - 24 hours \pm 3 hours after the 1st injection)

Twenty-four hours (± 3 hours) after the first injection, participants of the “Sentinel Groups” will be contacted by phone for the monitoring of AE; AESI and SAE. Any changes in the concomitant medications, medical status and occurrence of AE since the previous visit will be checked and recorded in the participant's source data and in the eCRF. In case of AE corresponding to the definition of SAE or AESI, an unscheduled visit will be organized in the investigational clinical site. At the end of the phone call, appointment for the visit 2 (day 7 ± 1) will be confirmed with the participant of the “Sentinel Groups”.

7.2.4. Visit 2 – “Sentinel Groups” (Day 7 ± 1 after injection)

This visit will take place 7 ± 1 after the first vaccination for participants of the “Sentinel Groups”. Participants will be interviewed by a physician, or his/her delegate, of the investigational clinical site about any changes in their medical status, concomitant medications and/or occurrence of any AEs, AESI an SAE since the last contact. Diaries will be reviewed and all AEs will be documented in participant’s source data and in the eCRFs.

The following assessment / activities will be performed during this visit

- Check if participant has met any individual halting rule
- Examination of the site of injection and assessment of local reaction.
- A directed physical examination

- Record of vital signs in sitting or supine position*
- Safety laboratory evaluations (blood and urine)
- Collection of saliva, urine, nasal swab and blood for shedding assessment

* *Vital signs can be measured in sitting or supine position as well as long as within 1 patient the measurements are always done in the same position.*

During the visit, the Investigator may order one re-test of the following parameters: vital signs (HR, RR, BP, body temperature), safety laboratory tests, if they need to evaluate the evolution of that parameter(s) or to confirm the value observed. The reason and results of this re-test will be documented in the participant's source data and in the eCRF.

At the end of the visit, the next visit (Visit 3) will be scheduled and confirmed with the participants of the "Sentinel Groups".

7.2.5. Visit 3 - Follow-up 1 (Day 14±1)

This visit will take place 14±1 days after the first vaccination. Participants will be interviewed by a physician, or his/her delegate, of the investigational clinical site about any changes in their medical status, concomitant medications and/or occurrence of any AEs, AESI an SAE since the last visit/contact. Diaries will be collected, reviewed and all AEs will be documented in participant's source data and in the eCRFs.

The following assessment / activities will be performed during this visit

- Check if participant has met any individual halting rule
- Examination of the site of injection and assessment of local reaction.
- Record of vital signs in sitting or supine position*.
- A directed physical examination.
- Safety laboratory evaluations (blood and urine).
- A blood sample will be drawn for immunomonitoring analysis.
- Saliva, Urine, nasal swab and an additional blood sample will be collected/drawn in the "Sentinel Groups" for shedding assessment.

* *Vital signs can be measured in sitting or supine position as well as long as within 1 patient the measurements are always done in the same position*

During the visit, the Investigator may order one re-test of the following parameters: vital signs (HR, RR, BP, body temperature), safety laboratory tests, if they need to evaluate the evolution of that parameter(s) or to confirm the value observed. The reason and results of this re-test will be documented in the participant's source data and in the eCRF.

At the end of the visit, the next visit (Visit 4) will be scheduled and confirmed with the participants.

7.2.6. Visit 4 - Second injection (Day 28±3)

This visit will take place 28±3 days after the first vaccination. Participants will be interviewed by a physician, or his/her delegate, of the investigational clinical site about any changes in their medical status, concomitant medications and/or occurrence of any AEs, AESI an SAE since the last visit.

The following assessment / activities will be performed during this visit and before the second injection

- Check if participant has met any individual halting rule
- Record of demographics (*only weight and BMI*).
- A directed physical examination.
- Record of vital signs in sitting or supine position*.
- Safety laboratory evaluations (blood and urine).
- Urine pregnancy test (For Females).
- Breath alcohol and urine drug tests (as outlined in Appendix 1)
- A blood sample will be drawn for immunomonitoring analysis.
- Saliva, Urine, nasal swab and an additional blood sample will be collected/drawn in the “Sentinel Groups” for shedding assessment.

* *Vital signs can be measured in sitting or supine position as well as long as within 1 patient the measurements are always done in the same position*

During the visit, the Investigator may order one re-test of the following parameters: demographics (Weight and BMI), vital signs (HR, RR, BP, body temperature), safety laboratory tests, urine pregnancy test (for females), breath alcohol and/or urine drug tests, if they need to evaluate the evolution of that parameter(s) or to confirm the value observed. Results of this re-test must be available prior to the second administration of the investigational product. The reason and results of this re-test will be documented in the participant's source data and in the eCRF.

If, no significant change in the participant's health since the last visit, he/she will receive the second intramuscular injection into the deltoid muscle of the opposite arm of the first injection ideally. The time and the arm (left or right) in which the vaccine was injected will be recorded in the participant's source data and in the eCRF.

In case of presence of a clinically significant acute disease at the time of vaccination or presence of fever defined by a body temperature $\geq 38.0^{\circ}\text{C}$ 24 hours prior to the visit or at the time of vaccination, the participant may be vaccinated at a later date, at the discretion of the Investigator or withdrawn from the study if he/she has met an individual halting rules (see section 4.8). The subject must be followed until resolution of the event.

After injection, the participants will remain in the Investigational clinical site for medical supervision and monitoring for a minimum of 1 hour after injection.

The following assessment / activities will be performed 1 hour (± 15 min) after the second injection:

- Vital signs in sitting or supine position*.
- Local reaction of the injection site.

Participant will be provided with a new diary for the 14±1 following days. At the end of the visit, which lasts approximately 2 hours and once the study physician has determined that he/she is fit to be released, the participant will be discharged from the Investigational clinical site. The appointment for the phone call 2 will be scheduled and confirmed with the participants of the “Sentinel Groups and the appointment for the Visit 5 (Day 42) will be scheduled and confirmed with the participants of the “Main Cohorts.

7.2.7. Phone call 2 - “Sentinel Groups” (Day 29 - 24 hours ±3 hours after 2nd injection)

Twenty-four hours (±3 hours) after the second injection, participants of the “Sentinel Groups” will be contacted by phone for the monitoring of AE; AESI and SAE. Any changes in the concomitant medications, medical status and occurrence of AEs, AESI and SAE since the previous visit will be checked and recorded in the participant's source data and in the eCRF. In case of AE corresponding to the definition of SAE or AESI, an unscheduled visit will be organized at the investigational clinical site. Appointment for the visit 5 (day 42) will be confirmed with the participant.

7.2.8. Visit 5 - Follow-up 2 (Day 42±3)

This visit will take place 42±3 days after the first injection. Participants will be interviewed by a physician, or his/her delegate, of the investigational clinical site about any changes in their medical status, concomitant medications and/or occurrence of AEs, AESI and SAE since the last contact. Diaries will be collected, reviewed and all AEs will be documented in participant's source data and in the CRFs.

The following assessment / activities will be performed during this visit

- Check if participant has met any individual halting rule
- Examination of the site of injection and assessment of local reaction.
- Record of vital signs in sitting or supine position*.
- A blood sample will be drawn for immunomonitoring analysis

* *Vital signs can be measured in sitting or supine position as well as long as within 1 patient the measurements are always done in the same position.*

During the visit, the Investigator may order one re-test of the following parameters: vital signs (HR, RR, BP, body temperature), if they need to evaluate the evolution of that parameter(s) or to confirm the value observed. The reason and results of this re-test will be documented in the participant's source data and in the eCRF

Saliva, Urine, nasal swab and an additional blood sample will be collected/drawn in the “Sentinel Groups” for shedding assessment.

At the end of the visit, the next visit (Visit 6) will be scheduled and confirmed.

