| 
17. DSMB
 | 
An independent DSMB will be installed to review accruing safety information, and if necessary, to determine whether study or individual participant halting rules have been met. The DSMB will review listings and summary tabulations of SAEs, deaths, AESIs, solicited AEs, unsolicited AEs and AEs leading to withdrawal from further vaccination.
 
A DSMB meeting, to review the safety data to evaluate the safety of the unblinded sentinel subjects before giving a positive recommendation for continuing with the blinded treatment phase will be performed once all six participants enrolled in the unblinded COVID-19 vaccine groups completed day 14 (V3). A Medical review of safety data (Intermediate Report 2, IR2, see below) will be performed after all six sentinel subjects completed day 42 (V5 – 14 days after the second injection). In case of any safety concern, an ad hoc DSMB meeting will be organized before giving a positive recommendation for continuing with the second injection of the “main cohorts”.
 
Additionally, the intermediate and interim analysis reports prepared at the following time points and will be shared with the DSMB (excluding observing DSMB members who will only have access to blinded safety report) and with the vaccine developer:
 
 1. Intermediate Report 1 (IR1): After all six sentinel subjects completed visit 4 (day 28) 2. Intermediate Report 2 (IR2): After all six sentinel subjects completed visit 5 (day 42), as outlined above 3. Intermediate Report 3 (IR3): After all (or at least 50% depending on the enrolment rate) subjects completed visit 4 (day 28) 
A final DSMB meeting will be organized after all subjects completed visit 8 (day 210) to be informed of the study global results.
 
Upon Sponsor decision ad hoc DSMB meetings might be scheduled during the whole duration of the study. A written DSMB charter will be developed. DSMB recommendations will also be transmitted to the Competent Authorities, the vaccine developer’s representative, and IRB-Institut Pasteur.
 |

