2.2. Outcomes

2.2.1. Primary outcome measures

- Rate of solicited Adverse Event up to 14 days after each injection.
- Rate of unsolicited AE up to 28 days after each injection.
- Rate of serious adverse events (SAEs) serious adverse reactions (SARs), suspected unexpected serious adverse reactions (SUSARs) and adverse events of special interest (AESI) all along the study period.

Safety and tolerability will be assessed after each vaccination and participants will remain under observation at the study site for at least one hour for presence of any acute reactions and solicited events and by means of a diary completed by the participants for 14 days after each vaccination (from day 0 up to day 14 and from day 28 up to day 42). For each AE/SAE/AESI, the intensity and the relationship to vaccination will be reported and will be evaluated by the investigator.

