7.2.9. Visit 6 - Follow-up 3/ End of Treatment phase (Day 56±3)

This visit will take place 56±3 days after the first injection. Participants will be interviewed by a physician, or his/her delegate, of the investigational clinical site about any changes in their medical status, concomitant medications AEs, AESI and SAE since the last visit.

The following assessment / activities will be performed during this visit

- Check if participant has met any individual halting rule
- Examination of the site of injection and assessment of local reaction.
- Record of demographics (*only weight and BMI*)
- A directed physical examination
- Record of vital signs in sitting or supine position*.
- Safety laboratory evaluations (blood and urine)
- Urine pregnancy test (For Females)
- A blood sample will be drawn for immunomonitoring analysis

* *Vital signs can be measured in sitting or supine position as well as long as within 1 patient the measurements are always done in the same position.*

During the visit, the Investigator may order one re-test of the following parameters: Demographics (Weight and BMI), vital signs (HR, RR, BP, body temperature), safety laboratory tests, urine pregnancy test (for females) if they need to evaluate the evolution of that parameter(s) or to confirm the value observed. The reason and results of this re-test will be documented in the participant's source data and in the eCRF.

At the end of the visit, the next visit (Visit 7) will be scheduled and confirmed with the participant.

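### Visit 5 is timed from the first injection, so it can fall 8 to 20 days after the second, and the 14-day solicited-event diary collected there can be cut short

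*Protocol*

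**What the plan says.** Protocol section 7.2.6 places the second injection at Visit 4: "This visit will take place 28±3 days after the first vaccination". Section 7.2.8 places Visit 5 on the same clock: "This visit will take place 42±3 days after the first injection". If the participant is acutely ill or febrile at Visit 4, section 7.2.6 says that "the participant may be vaccinated at a later date, at the discretion of the Investigator"; it gives no limit, and neither it nor section 7.2.8 says whether Visit 5 then moves.

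Other parts of the protocol count from the second injection:

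- Section 2.2.1, first primary outcome: "Rate of solicited Adverse Event up to 14 days after each injection". Section 9.1.12.1 sets the investigator the same 14-day reporting period.
- Section 7.1, footnote 4, on the diary: "filled in up to 14±1 days after each vaccination, retrieved at V3 and V5". Sections 7.2.6 and 8.2 repeat the 14±1-day length, and section 7.2.8 has the diary collected at Visit 5.
- Synopsis item 17 ties the sentinel safety review to the point when all six sentinels have "completed day 42 (V5 – 14 days after the second injection".

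After the first injection the matching visit is held tightly. Section 7.2.5 says: "This visit will take place 14±1 days after the first vaccination".

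**The concern.** The statements about Visit 5 agree only if Visits 4 and 5 both fall on their nominal days. Each may move by 3 days in either direction, and the interval between them is not controlled. A late second injection followed by an early Visit 5 obeys both visit windows, yet brings the diary in well before day 14.

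Three things depend on that interval:

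- **Primary endpoint data.** Section 2.2.1 names the diary as the participant's instrument for solicited events over 14 days. If it is collected early, the remaining days have no daily record.
- **Sentinel review.** The day-42 review exists to judge the safety of the second injection before the main cohorts receive theirs (sections 3.2 and 4.12). It covers three participants per dose level, so lost days matter.
- **Shedding.** The Visit 4 sample is taken before the second injection (section 7.2.6), and none is scheduled after Visit 5 (section 8.3). Visit 5 is therefore the only look at shedding after dose 2.

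A statistical analysis plan can re-window data, but it cannot recover diary days that were never filled in.

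**Working it through.** **Inputs, in days after injection 1**

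- Visit 4 (injection 2): 28±3, so day 25 to 31 (section 7.2.6).
- Visit 5: 42±3, so day 39 to 45 (section 7.2.8).
- Diary tolerance: 14±1, so 13 to 15 days after an injection (section 7.1, footnote 4).

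**The plan's own figure.** On nominal days the interval is 42 − 28 = 14 days, which matches the synopsis.

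**Range under the permitted windows**

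- Shortest: 39 − 31 = 8 days.
- Longest: 45 − 25 = 20 days.
- Largest diary shortfall against 14 days: 14 − 8 = 6 days.
- Comparison after injection 1: Visit 3 falls at 13 to 15 days.

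The 20-day end applies to the visit and its samples. The diary stops at 14±1 days, so its coverage runs from 8 to about 15 days.

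**Count of permitted day pairs.** Let *a* and *b* be the departures of Visits 4 and 5 from nominal, each from −3 to +3. The interval is 14 + (*b* − *a*). There are 7 × 7 = 49 pairs, and a difference *d* = *b* − *a* arises in 7 − |*d*| of them.

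| Interval after injection 2 | Pairs |
|---|---|
| under 14 days (*d* ≤ −1) | 6+5+4+3+2+1 = 21 |
| under 13 days (*d* ≤ −2) | 5+4+3+2+1 = 15 |
| over 15 days (*d* ≥ 2) | 5+4+3+2+1 = 15 |

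The 15 pairs under 13 days breach the diary's own tolerance.

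**Deferred second injection, Visit 5 not moved**

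- The last permitted Visit 5 is day 45. A full 14 days is possible only if injection 2 is given by day 45 − 14 = 31, and 13 days only if it is given by day 45 − 13 = 32.
- As an assumed example, injection 2 on day 35 puts Visit 5 at 39 − 35 = 4 to 45 − 35 = 10 days.

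Eight days is therefore not a floor.

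**After re-timing.** With Visit 5 at 14 to 17 days after the actual second injection, and injection 2 within its window, Visit 5 falls on day 25 + 14 = 39 to 31 + 17 = 48.

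**The case against.** The strongest reply is that a site can satisfy every rule at once. The main-cohort Visit 5 appointment is made at Visit 4, when the date of injection 2 is known, and the diary rule asks for 14±1 days. For any second injection given by day 31, some permitted Visit 5 date reaches 14 days. On this reading the 8-day case needs someone to overlook the diary rule. That is fair, and it is why the shortfall is possible rather than certain. But the visit section gives the shorter interval as compliant, nothing says which rule prevails, and beyond day 32 no Visit 5 date within its stated window meets the diary tolerance.

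A second reply is that the events are not lost. The endpoint remains 14 days, adverse events are recorded throughout the study (sections 8.1.1 and 9.1.12.1), and Visit 6 asks about events since the last visit and re-examines the injection site (section 7.2.9). This also stands in part: what an early Visit 5 costs is the prospective daily record, which recall replaces.

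Third, all blinded arms, placebo and cohort C included, have two injections and the same windows (section 4.11), and section 12.3 compares treatment groups, not doses. Any shortfall should therefore be similar across arms. That stands, and it limits the harm to the completeness of dose-2 data relative to dose 1.

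**Conclusion.** The point holds as an internal conflict that should be fixed; it does not undermine the trial's comparisons. Visit 5 can be 8 to 20 days after the second injection within the stated windows, and earlier if the injection is deferred and the visit is not moved. Daily capture of solicited events after dose 2 can lose up to 6 days within the windows. How often this would happen cannot be said from the protocol: the 21 and 15 of 49 are counts of permitted pairs, and turning them into percentages of participants would need a distribution of visit dates that is not given.

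Three stronger readings are tempting but not supported:

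- **Visit 6 truncates the 28-day unsolicited-event count.** Section 7.2.9 times Visit 6 the same way ("This visit will take place 56±3 days after the first injection"), so it can fall 53 − 31 = 22 to 59 − 25 = 34 days after injection 2. But unsolicited events are recorded continuously to the end of the study, so an early Visit 6 does not cut the count.
- **Visit 3 on day 13 is an error.** It lies within the stated 14±1-day diary tolerance.
- **The between-arm safety comparison is biased.** The visit windows are common to all blinded arms, and the protocol gives no ground to expect a differential effect.

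**What to change.** Time Visit 5 from the actual date of injection 2, no earlier than 14 days after it (for example 14 to 17 days), and say that this applies when injection 2 is deferred. Collect the second diary only once day 14 is complete; if the visit happens earlier, finish the diary remotely. Bring synopsis item 17, section 2.2.1 (which also gives the diary periods as fixed study days), section 7.1 footnote 4 and sections 7.2.6 and 7.2.8 into line. The amendment should also say how Visits 5 and 6 are ordered after a long deferral: an injection on day 39 would put Visit 5 at day 53 or later, inside the Visit 6 window.

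Keep the immunogenicity analysis by scheduled study visit. Analysing by days since the last injection would be wrong for cohort C, whose second injection is placebo (section 3.3, Table 1).

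The cost is an amended visit table and scheduling tool, with no added visits. The example window has 4 permitted days instead of 7. Visit 5 would spread over about day 39 to 48 from injection 1 instead of 39 to 45. That slightly loosens cohort C's timing after its only vaccine dose and could delay the sentinel review by up to 48 − 45 = 3 days.
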